9.1.9 Discontinuation and Withdrawal

Participants who discontinue study treatment prior to completion of the treatment period should be encouraged to continue to be followed for all remaining study visits.

When a participant withdraws from participation in the study, all applicable activities scheduled for the Early Discontinuation visit as described in the SoA (Section 2) should be performed (at the time of withdrawal). Any adverse events which are present at the time of withdrawal should be followed in accordance with the safety requirements outlined in Section 9.3.

9.1.9.1 Withdrawal From Future Biomedical Research

Participants may withdraw their consent for Future Biomedical Research. Participants may withdraw consent at any time by contacting the principal investigator for the main study. If medical records for the main study are still available, the investigator will contact the Sponsor using the designated mailbox ([contact]). Subsequently, the participant's consent for Future Biomedical Research will be withdrawn. A letter will be sent from the Sponsor to the investigator confirming the withdrawal. It is the responsibility of the investigator to inform the participant of completion of withdrawal. Any analyses in progress at the time of request for withdrawal or already performed prior to the request being received by the Sponsor will continue to be used as part of the overall research study data and results. No new analyses would be generated after the request is received.

In the event that the medical records for the main study are no longer available (eg, if the investigator is no longer required by regulatory authorities to retain the main study records) or the specimens have been completely anonymized, there will no longer be a link between the participant's personal information and their specimens. In this situation, the request for specimen withdrawal cannot be processed.

9.1.10 Participant Blinding/Unblinding

Participants whose treatment assignment has been unblinded by the investigator/delegate and/or non-study treating physician must be discontinued from study treatment, but should continue to be monitored in the study.

Additionally, the investigator must go into the IRT system and perform the unblind in the IRT system to update drug disposition. In the event that the emergency unblinding call center is not available for a given site in this study, the IRT system should be used for emergency unblinding in the event that this is required for participant safety.

Study treatment identification information is to be unmasked ONLY if necessary for the welfare of the participant. Every effort should be made not to unblind the participant unless necessary.

In the event that unblinding has occurred, the circumstances around the unblinding (eg, date, reason and person performing the unblinding) must be documented promptly, and the Sponsor Clinical Director notified as soon as possible. Only the principal investigator or delegate and the respective participant's code should be unblinded. Other study site personnel and Sponsor personnel directly associated with the conduct of the study should not be unblinded.

9.1.11 Domiciling

On Day -2 of the screening period, eligible participants will be admitted to the study clinic and remain confined to the clinic until completion of the treatment period on Day 7 (Section 5.1).

Note: Participants who fail screening between Day -2 and Day 1 (prior to randomization) will be discharged from the clinic and *excluded* from the trial.

Participants who lack confirmation of HRV-16 shedding by nasal swab testing within 72 hours of inoculation will be notified (once results are available), discontinued from study treatment, have discontinuation procedures performed (as specified in the SoA [Section 2]), and be discharged from the clinic; a safety follow-up telephone call will be performed 14 days after the last dose of study treatment.

9.1.12 Calibration of Critical Equipment

The investigator or qualified designee has the responsibility to ensure that any critical device or instrument used for a clinical evaluation/test during a clinical study that provides important information about inclusion/exclusion criteria and/or safety or efficacy parameters shall be suitably calibrated and maintained to ensure that the data obtained is reliable and/or reproducible. Documentation of equipment calibration must be retained as source documentation at the study site.

Critical Equipment for this study includes:

- VitaloJAK™ cough monitor (study sourced): Calibration by the site is not necessary (See VitaloJAK™ Site Manual)
- Spirometer (site equipment): The spirometer should be calibrated according to American Thoracic Society/European Respiratory Society (ATS/ERS) guidelines. Calibration checks should be performed (ie, with a 3-liter syringe) at a minimum of each day that a trial participant performs a spirometry assessment. The calibration check records should be printed and kept in a reviewable log. It is preferred that the calibration syringe used to check calibration of the spirometer also be subjected to a validated calibration according to the manufacturer's specifications.
- ECG machine (site equipment): Calibration should be performed according to the manufacturer's specifications.
- Equipment for Cough Challenge (locally sourced): Calibration should be performed according to the manufacturer's specifications.
- Equipment for HRV-16 administration (locally sourced): Calibration should be performed according to the manufacturer's specifications as necessary.

9.1.13 Other Study Procedures

9.1.13.1 Antibody Titers to Human Rhinovirus Type 16

Sample collection, storage, and shipment instructions to quantify antibody titers for HRV-16 at the Screening Visit are provided in the Central Laboratory Manual.

9.1.13.2 Ethanol Breath Test

The ethanol breath test, commonly known as alcohol breath test, will be performed at the site, as specified in the SoA (Section 2), to determine the level of ethanol in the blood. Alcohol in the mouth gives a rapid peak in ethanol concentration on the evidential test.

9.1.13.3 Urine Cotinine Test

Urine cotinine testing will be performed, as specified in the SoA (Section 2), to determine use of tobacco products by biochemical measurement of cotinine (nicotine metabolite) in a urine specimen.

9.1.13.4 Nasal Swabs for Human Rhinovirus Polymerase Chain Reaction

During the treatment period, experienced site staff will collect nasopharyngeal swabs from each participant every 12 hours for the 72-hour period immediately following inoculation with HRV-16, as specified in the SoA (Section 2). Instructions for collection, storage, and handling/shipment of nasal swab specimen and testing for HRV-16 by polymerase chain reaction (PCR) are provided in the Central Laboratory Manual.

9.2 Efficacy Assessments

Compliance with the efficacy and safety assessments (along with study treatment use) is essential, and any non-compliance noted by the investigator or designee should result in consultation with the participant on corrective measures needed to ensure compliance.

9.2.1 Cough Monitoring – VitaloJAK™ Recording Device

The assessment of awake coughs per hour (based on 24-hour sound recordings) will be evaluated using the VitaloJAK™ cough monitor, a 510k approved (Premarket Notification per the United States Food, Drug and Cosmetic Act) that has been implemented successfully in clinical studies of potential cough therapies, including two Phase 2 studies of MK-7264.

The VitaloJAK™ cough monitor recording device uses two input channels. The first channel records sounds from the lungs and trachea through a chest contact sensor, which is attached to the skin at the top of the sternum with adhesive. The second channel captures ambient sounds through a lapel air microphone. Sounds are stored on a high-capacity compact flash (CF) II card. The device will be carried in a cloth belt bag worn around the participant's waist, and it will record all sounds the participant makes during cough monitoring.

When the digital recording arrives at the central reading center, a human analyst uses standardized criteria to identify transitions between awake and asleep states. To reduce review time, the 24-hour recordings are processed through a computerized algorithm that

removes periods of silence and a high proportion of non-cough sounds. A cough analyst then evaluates the abbreviated recording by listening to both audio channels and inspecting the visual wave form of potential cough sounds. The analyst tags the explosive portion of each cough using the Vitalograph Web Portal for analysis and annotation of sound recordings. Cough counts are then tallied automatically from the annotated audio file.

During the Treatment Period, the cough monitor will be attached to all randomized participants and set up prior to first dose of study treatment (see Section 9.10.2 and the VitaloJAK™ Site Manual for further details). The monitor will be set to begin recording immediately after the first morning dose. The device will be worn 24 hours a day for the 7-day treatment period with approximately 15 minutes/day "off-time" permitted for showering. Participants will continue to wear the cough monitor during the cough challenge procedures on Days 1, 4, and 7, as the cough counting data from the cough monitor will be used to support the primary analysis.

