Urine Drug Screen (UDS)	X													Performed at site locally. Additional UDS can be performed for cause during the study, at the investigator's discretion .
Nasal Swabs for HRV 16 polymerase chain reaction (PCR)				X	X	X								After inoculation of HRV-16, nasal swabs are collected every 12 hours for 72 hours (Day 1 to Day 3)
Efficacy Procedures														
Attach Cough Monitor				X										Just prior to inoculation with HRV-16
Remove Cough Monitor											X			
Cough Monitoring				X	X	X	X	X	X	X				Cough monitoring using cough monitor device (VitaloJAK™) begins after first dose of study treatment on Day 1 through Day 7 or early discontinuation.
Adenosine Triphosphate (ATP) Cough Challenge			X	X			X			X				Manual cough monitoring is performed during ATP cough challenge at designated visits only during Stage 1. On Days 1, 4, and 7, it is performed 2 hours (± 30 min) post-morning dose.

Study Period	Screening			Treatment							Dis-charge	Telephone Follow-Up (14 days post last dose)	Early Discontinuation	Notes
		Bas e-line	Random -ization											
Visit Number/Title	1	2	3	4	5	6	7	8	9	10	11			
Scheduled Day and Window:	Day -28 to Day -3	Day -2	Day -1	Day 1	Day 2	Day 3	Day 4	Day 5	Day 6	Day 7	Day 8	Day 22 (+ 3 days)	Between Days 1 and 7	
Collect Previous Cough Monitor Data					X	X	X	X	X	X	X		X	Collect compact flash (CF) memory card from cough monitor and insert new CF card and new battery pack every ~ 24 hours
Cough Severity Visual Analog Scale (VAS)			X	X	X	X	X	X	X	X				Completed in the evening
Cough Severity Diary (CSD)			X	X	X	X	X	X	X	X				Completed in the evening
Leicester Cough Questionnaire-Acute (LCQ-acute)			X	X	X	X	X	X	X	X				Completed in the evening
Wisconsin Upper Respiratory Syndrome Symptom Survey (WURSS-24)			X	X	X	X	X	X	X	X				Completed in the evening
Safety Procedures														
Full Physical Examination	X										X		X	Refer to Section 9.5.1 for details
Height & Weight	X		X								X		X	Day -1, Day 8, and Early Discontinuation Visit: weight only
Vital Signs (heart rate, blood pressure, respiratory rate, and temperature)	X	X	X	X	X	X	X	X	X	X	X		X	All visits during Treatment Period: predose
12-lead Electrocardiogram (ECG)	X		X								X		X	Performed with site equipment
Spirometry	X													Performed with site equipment
Hematology	X			X						X			X	Days 1 and 7: premorning dose
Urinalysis	X			X						X			X	Days 1 and 7: premorning dose

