The Cough Severity VAS is a single-item questionnaire asking the participant to rate the severity of their cough "today" using a 100 mm VAS anchored with "No Cough" at 0 and "Extremely Severe Cough" at 100. Similar to the well-established use of VAS in chronic pain, the Cough Severity VAS provides a quick and easily interpreted subjective assessment to monitor improvement of acute cough during treatment.

The CSD is a 7-item, disease-specific PRO measure with a recall period of "today". The measure evaluates three domains: frequency of cough (3 items), intensity of cough (2 items), and disruption due to cough (2 items); each item is rated on an 11-point scale ranging from 0 to 10, with higher scores indicating greater severity. A CSD total score and 3 domain scores (ie, frequency, intensity, disruption) can be calculated.

The LCQ-acute is a 19-item health-related quality-of-life (HRQoL) questionnaire specific for acute cough which contains three domains (ie, physical, psychological, and social), calculated as a mean score for each domain ranging from 1 to 7 and total score ranging from 3 to 21. Each item on the LCQ-acute assesses symptoms or the impact of symptoms on HRQoL in the last 24 hours using a 7-point Likert scale ranging from 1 to 7. Higher scores indicate better HRQoL.

The following exploratory efficacy endpoints will also be measured:

1. 24-hour cough count (based on 24-hour sound recordings) on Day 3
2. Awake cough count on Days 1, 2, 4, 5, 6, 7
3. Wisconsin Upper Respiratory Syndrome Symptom Survey (WURSS-24) as change from baseline on Day 3
4. Cough reflex sensitivity (C2 and C5 on Days 1, 4, and 7) measured by standardized methodology incorporating an ATP cough challenge (Stage 1 only)

The WURSS-24 is a 24-item HRQoL questionnaire specific for acute upper respiratory infection, including influenza-like symptoms. The WURSS-24 assesses symptoms or the impact of symptoms on HRQoL ‘over the last 24 hours’ using an 8-point Likert scale ranging from 0 to 7. Higher scores indicate worse HRQoL.

MK-7264 has been shown to reduce cough reflex sensitivity, as measured by ATP cough challenges, in healthy participants as well as participants with chronic cough [IB Edition 16 2017]. Stage 1 of P013 will evaluate whether similar effects also occur in participants with acute cough.

The secondary and exploratory efficacy endpoints will add supportive information to the primary efficacy endpoint of awake coughs per hour on Day 3 of treatment.

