9.2.3 ATP Cough Challenge (Stage 1 Only)

Cough reflex sensitivity is measured by standard clinical methodology incorporating ATP cough challenge in accordance with the Procedures Manual. The ATP cough challenge will be administered ONLY during Stage 1 of the trial.

The standard endpoints measured in cough challenge testing are reflex sensitivity to ATP measured by C2 and C5 (ie, concentration of cough challenge agent [ATP] inducing at least 2 or 5 coughs, respectively) during Stage 1 on Days -1, 1, 4, and 7.

The number of coughs during the ATP cough challenge will be assessed manually by site staff during all ATP cough challenges.

Participants will continue to wear the cough monitor during the cough challenge procedures on Days 1, 3, and 7, as the cough counting data from the cough monitor will be used to support the primary analysis. All analyses related to the ATP cough challenge will be performed using manual cough counting data, including the exploratory analysis related to cough reflex sensitivity.

The challenge should be discontinued for the day if a participant experiences severe side effects or coughs excessively and makes a clear request to stop taking the challenge test (see Procedures Manual).

β -agonist should be available for participants who experience bronchoconstriction; other appropriate medical interventions should be provided as necessary. Those who need to discontinue the cough challenge may still participate in the cough challenges on subsequent days.

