10.4.4 Derivations of Efficacy Endpoints

The primary efficacy endpoint of this study is the awake coughs per hour on Day 3 of the treatment period. It is calculated as:

Awake coughs per hour = Total number of cough events during the monitoring period (24-hour interval) the participant is awake / Total duration (in hours) for the monitoring period the participant is awake

Awake is time between waking up and sleep during the 24-hour monitoring period.

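### Coughs provoked by the Stage 1 ATP challenge are counted in the exploratory awake cough frequencies on Days 1, 4 and 7, and one sentence of Section 9.2.3 puts a challenge on Day 3, the primary endpoint day

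*Combined protocol and SAP*

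**What the plan says.** Section 9.2.1 keeps the device on during the challenges ("Participants will continue to wear the cough monitor during the cough challenge procedures on Days 1, 4, and 7, as the cough counting data" are to support the primary analysis) and says of the device that "it will record all sounds the participant makes during cough monitoring". Section 9.2.3 bases all challenge analyses on manual counts, so C2 and C5 do not need the device data from the session.

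Section 10.4.4 takes as the numerator of awake coughs per hour "Total number of cough events during the monitoring period (24-hour interval) the participant is awake" and divides by all awake hours. It contains no exclusion for the challenge.

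Section 4 makes awake cough frequency on Days 1, 2, 4, 5, 6 and 7 exploratory and on Day 3 primary. Section 10.6.1 puts every post-baseline daily value into the primary longitudinal model, which has treatment-by-visit terms and unstructured covariance but no term for stage or challenge.

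On timing, the Schedule of Activities says: "On Days 1, 4, and 7, it is performed 2 hours (± 30 min) post-morning dose". The endpoint sentence of Section 9.2.3 places C2 and C5 "during Stage 1 on Days -1, 1, 4, and 7". Two paragraphs later the same section says: "Participants will continue to wear the cough monitor during the cough challenge procedures on Days 1, 3, and 7".

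On the drug, Section 5.4.3.1 says: "MK-7264 has been shown to reduce cough reflex sensitivity, as measured by ATP cough challenges".

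**The concern.** Awake cough frequency is meant to describe cough from the induced infection. On a challenge day it also contains coughs that the site provoked. There are reasons to expect this part to differ by arm. The drug is said to reduce reflex sensitivity to ATP, the challenge comes about 2 hours after a dose whose median Tmax is 1 to 2 hours (Section 5.5.1), and only some 5% to 10% of participants are expected not to respond at screening (Section 5.4.2). Suppression of an experimental stimulus could then be read as suppression of viral cough. The distortion would weigh most where illness cough is low, and Section 5.4.1 expects symptoms to have largely gone by about Day 7.

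The challenge is confined to Stage 1, so a 15 mg arm added in Stage 2 would be compared with a placebo group of which only part was challenged.

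The sentence naming Day 3 raises the stakes. Day 3 is the primary endpoint and the basis of the interim rule (Section 10.7.1), and every participant in that interim analysis is a Stage 1 participant.

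**Working it through.** **Arm sizes.** Section 7.3 gives 25 per arm in Stage 1. In the three-arm case Stage 2 has 150 − 50 = 100 participants, split 1:2:1 as 25/50/25. Adding Stage 1 gives 50 per group and 150 in total, which agrees with Table 10. Evaluable participants are 50 × (1 − 0.20) = 40 per group, which agrees with Section 10.9.

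**Share of each arm challenged.** For 45 mg and placebo: 25/50 = 0.50 at 50 per arm and 25/94 = 0.266 at 94 per arm. For 15 mg: 0/50 = 0.

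**Assumptions, not in the documents.** E is the number of provoked coughs per session on placebo (10 to 50), H the awake hours (16), and f the proportional reduction in provoked coughs on 45 mg (25% to 75%).

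**Level.** Each challenged placebo participant's value rises by E/H: 10/16 = 0.625, 20/16 = 1.25, 50/16 = 3.125 coughs/h. At E = 20, H = 14 gives 1.43 and H = 18 gives 1.11.

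**45 mg minus placebo on a challenge day.** Stage 1: −fE/H. Pooled: the same times the challenged share.

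| E | f | Stage 1 | Pooled, total 100 | Pooled, total 188 |
|---|---|---|---|---|
| 10 | 25% | −0.16 | −0.08 | −0.04 |
| 20 | 50% | −0.625 | −0.31 | −0.17 |
| 50 | 75% | −2.34 | −1.17 | −0.62 |

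**15 mg minus pooled placebo on a challenge day.** −0.50 × E/H, with no drug effect assumed: −0.31, −0.625 and −1.56 coughs/h for E = 10, 20 and 50.

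**Effect on the Day 3 contrast.** With a separate treatment contrast at each visit, unstructured covariance and complete data, the Day 3 estimate is the Day 3 difference in means, so other days cannot move it. A simulation checked this: 40 per arm, half of each arm challenged, 20 provoked coughs on placebo and 10 on 45 mg, H = 16, true difference −1.5, no gender or site terms.

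- Challenges on Days 1, 4 and 7, complete data: Day 3 contrast −1.523 without and −1.523 with contamination. With 10% of values missing at random: −1.536 and −1.539. The contrasts on Days 1, 4 and 7 each moved by about −0.31.
- Challenges on Days 1, 3 and 7, complete data: Day 3 contrast −1.657 without and −1.967 with contamination, a shift of −0.31. With 10% missing: −1.520 and −1.837, a shift of about −0.32.

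The interim analysis uses Stage 1 alone, so a Day 3 challenge would move it by the undiluted −0.5 × 20/16 = −0.625 on the same assumptions.

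**Which recording holds the Day 4 challenge.** If recording starts at the first dose and cards are changed every 24 hours, the third recording covers hours 48 to 72. With the Day 4 dose at the same clock time as on Day 1, the challenge starts at 72 + 2 ± 0.5, that is at 73.5 to 74.5 hours, outside the third recording.

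**The case against.** The case against a serious finding is strong on the primary endpoint, and most of it stands.

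- *Day 3 challenge.* A reader might infer from Section 9.2.3 that a Day 3 challenge is planned. That sentence concerns wearing the monitor, and it is contradicted by the same section's endpoint sentence, Section 9.2.1, Section 4, Section 5.4.3.1 and the Schedule of Activities. It establishes a contradiction to be reconciled. It does not establish a biased primary endpoint.
- *Primary model.* A reader might infer that contaminated days bias Day 3 because they enter the same response vector. Treatment-by-visit terms and unstructured covariance prevent this almost entirely. The Toeplitz fallback was not checked.
- *Card spillover.* A Day 4 challenge could fall in the third recording if dosing moved 1.5 to 2.5 hours earlier by the clock. Section 9.1.8.1 asks for approximately the same dosing times each day, so this would be a departure from the plan.
- *Direction.* A reader might infer that the documents show a bias in favour of the drug. Section 5.4.3.1 speaks of reflex sensitivity, measured as the concentration that provokes 2 or 5 coughs. With rising concentrations, a higher threshold can mean more steps and need not mean fewer coughs in total.
- *Scope.* Section 10.4.4 introduces its formula for Day 3, so its use on other days is an inference, though a natural one. Exploratory methods are deferred to the sSAP and challenge details to the Procedures Manual. Either could hold an exclusion that is not visible here.

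What survives is that the protocol and SAP text removes nothing, and the affected results are planned ones.

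**Conclusion.** As written, provoked coughs enter the Stage 1 awake cough frequencies on Days 1, 4 and 7. These are exploratory endpoints in a trial without hypotheses, so this should be fixed but does not threaten the primary result under the Day 1, 4 and 7 schedule.

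A false difference between 45 mg and placebo of 0.16 to 2.34 coughs/h in Stage 1 rests wholly on the assumed E, H and f. It would be nil if total provoked coughs did not differ by arm, and it could reverse sign. The imbalance between 15 mg and pooled placebo (0.31 to 1.56 coughs/h for E = 10 to 50) needs no drug effect, but arises only if that arm is added and the stages are pooled.

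The primary endpoint and the interim decision are at risk only if a challenge is actually done on Day 3, which one sentence of Section 9.2.3 would allow. That sentence is current text and cannot be left unresolved.

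**What to change.** - Record the start and stop time of every challenge on the eCRF.
- State in Section 10.4.4, for all days, that the challenge session plus a pre-stated margin is removed from both the cough count and the hours in the denominator. Apply this to awake and 24-hour frequency, on whichever recording the session falls.
- Add a sensitivity analysis that keeps the session in.
- Reconcile Section 9.2.3 with Section 9.2.1, Section 4 and the Schedule of Activities on the challenge days before Stage 1 starts.

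The cost is two eCRF times per session, one derivation rule, a short text correction, and a short loss of recorded time on three days in Stage 1. The documents do not give the session length. The sample size does not change. The times need to be captured prospectively, because exact removal may not be possible afterwards.
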